home in a naturalistic setting: Week 1-Session 1, WP smokers will smoke using 1 quick-light charcoal and room temperature water in the WP jar, Week 2-Session 2, WP smokers will smoke using 1 quick-light charcoal but adding ice cubes to the water in the WP jar, Week 3-Training for session 3, RAs will train participants on how to use a charcoal-free electrically heated WP head to heat the tobacco, and Week 4-Session 3, WP smokers will smoke WP tobacco without charcoal using the electric WP head and room temperature water. We will collect a) Tobacco Use History; b) 4-week Tobacco Use and Exposure Diaries; c) WP Smoking Session Day and Exposure Form; d) CO exposure: Micro+Smokerlyzer® CO monitor will be used for exhaled CO two minutes pre and post each smoking session; and e) 6 first morning urine samples: pre and post the 3 sessions to measure urinary cotinine, NNAL, 1-HOP, and SPMA. We will measure urinary Furan-BDA-NAL in WP smokers who smoke WP tobacco as commonly practiced using quick-light charcoal and room temperature water in the WP jar (urine samples from Session1).

Inclusion Criteria for Participants

Adult waterpipe smoker: A male or female, 18 years or older, who smokes WP tobacco exclusively, smokes at least 1 WP head per month, and smokes at least 1 WP head per WP smoking session, smokes WP at home, agrees to smoke *Starbuzz* WP tobacco, and lives in a 'smoker home'. Adult non-smoker: A male or female, 18 years or older, who lives in a 'non-smoker home'.

Inclusion Criteria for Homes

A Smoker Home: is a home in which residents have smoked WP tobacco exclusively indoors/outdoors at least in the last month. A Non-smoker Home: is a home where to the knowledge of the residents no smokers have lived in and no visitors had smoked indoors/outdoors in the past month, and where a potential nonsmoker participant who has not been exposed to any secondhand smoke at least in the last month resided full-time.

Exclusion Criteria

Adults with major physical/psychiatric illnesses that are judged by the research assistants (RAs) to interfere with ability to give informed consent or to successfully complete an interview will not be included in the study. Daily WP smokers will be excluded because they may not be able to adhere to the wash-out periods before the 3 WP sessions. Pregnant women are also excluded.

Screening Potential Participants

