The PI, study coordinator (SC), RAs and volunteering student interns will take part in all phases of the study. We have a collaborative relationship with SDSU internship faculty advisors. Potential participants will be approached at random in the community by the RAs accompanied by interns, and will obtain a verbal consent to complete a brief voluntary screening form which will be used to recruit individuals and determine their initial eligibility to participate in a SDSU research study. The PI will work closely with the SC and RAs to qualify participants. The RAs will contact initially qualified potential participants by phone and further determine their qualification by completing an eligibility checklist of inclusion and exclusion criteria. Qualified potential participants will be invited for an Office Visit at our research center for enrollment in the study.

The 4-Week Study period: comprised of 3 WP smoking sessions & 7-day activities per session (Table 2)

Waterpipe Smoking Session 1

Day 1 - Office Visit: The Office Visit is expected to take between 60 and 90 minutes. Trained by the PI, the SC and RAs will explain the 7-day study period activities for the 3 smoking sessions and consent form, answer all questions, and obtain a signed consent form. Thereafter, the RAs will give a saliva test to nonsmokers; interview participants face-to-

Table 6. Forms and measures for the 7-Day D	ata Colle	ction S	chedul	e for eacl	h of the	3 smoki	ng sessio	ns.
	Office visit			phone call 1		phone call 2	Home visit 1	Home visit 2
	Day 1	Day 2	Day 3	Day 4	Day 5	Day 6	Day 7	Day 8
Waterpipe Smoking Session Day							X	
Study Protocol and Consent Form	Х							
To bacco Use History Questionnaire	Х							
7-Day 24 hour Tobacco Use Diary	Х	Х	Х	Х	Х	X	Х	Х
7-Day 24 hour Tobacco Exposure Diary	Х	Х	Х	X	Х	X	Х	X
WP Smoking Session Day & Exposure Form							Х	
Provide First Morning Urine Samples							Х	Х
RAs Measure CO in exhaled breath							Х	
Illnesses & Medical Care History Form								X
RAs pick up urine samples							Х	X

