
Waterpipe Smoking Session 2. The 7-Day study activities: Days 1 through 7 are similar to session 1 with the exception that the RAs will add one tray of ice cubes and water in the WP jar. The RAs will arrange for a training session to use the charcoal-free electrically heated WP head.

Waterpipe Smoking Session 3. The 7-Day study activities: *Training for session 3.* Any day during the third week, the RAs will arrange to visit the participants to train them on the charcoal-free electrically heated WP head, and arrange for the 3rd smoking session using the electric head. *Smoking session 3*. Days 1 through 7 are similar to session 1 using room temperature water in the WP jar, however using the charcoal-free electrically heated WP head instead of using charcoal. During the last visit, the day after the 3rd smoking session, the RAs will interview participants to complete the *Illnesses and Health Care History Form* (completed during the last day of the study period to avoid biasing smoking behavior), pick up the final urine samples, thank the participants and inform them that they will receive a check from SDSU in the amount of \$250 by mail.

Standardized Setting of the Waterpipe Device, Smoking Protocol, Waterpipe Tobacco and Charcoal

To reduce variance of factors extraneous to our configurations of WP smoking practices, we will standardize setting the WP device, aluminum foil, and amount, type and brand of WP tobacco and quick-light charcoal. We will determine and standardize the volume and commercial brand of drinking water to be placed in the WP jar, and volume of water and added ice cubes to be standardized.

Waterpipe Device. We will purchase 10 new unused WPs similar in specification to the Battelle Research-grade WP: 2L glass water jar, 28.6 cm length of body. All WPs will be the same size, style, and brand. In the kitchen of the participants, before and after each use, the RAs will thoroughly clean the stem and glass jar with soap and water between sessions and between participants. Three new hoses will be used for each smoker.

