Smoking Protocol. During each WP smoking session, participants will be asked to smoke one WP tobacco head at their home as they normally do, not to share their WP with other smokers nor be in the presence of another smoker. WP smokers usually smoke 1 WP head per smoking session, ranging 30-60 minutes per session. At home of the participants, the RAs will set up the WP following a standardized protocol. Briefly, the RAs, wearing gloves at all times, will place room temperature commercial drinking water in the WP jar for sessions 1 and 3, and one tray of ice cubes and a standardized volume of water for session 2. The RAs will weight (using an analytical balance) and load one head of WP tobacco (10 gram Two Apples flavor, *Starbuzz* brand, U.S.), and cover it with a single (9x9 cm) aluminum sheet (manufacturer preperforated punch pattern). Using a portable lighter, the RAs will light a single quick-light charcoal (40 mm, *Three Kings* brand, Holland), and place it on the loaded WP head. At the conclusion of the smoking session, the RAs will weigh the remaining tobacco and charcoal, and complete the WP session observation form, such as length of time smoking, etc.

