Screening Form (face-to-face intercept interviews) will collect the name, e-mail address, telephone number, age, gender, smoking habits, and willingness to participate in the study. The RAs will request permission to contact them by phone to confirm eligibility using the inclusion and exclusion criteria. Consent Form is explained in detail in the 'Protection of Human Subjects form'. Tobacco Use History Questionnaire (face-to-face interview using a standardized protocol) Past 7 and 30 days use; average number of cigarettes and/or WP heads and length of time smoked per typical work and nonwork day; past 7 and 30 days secondhand exposure, e.g. average number of WPs and/or cigarettes exposed to per day at home, at work and elsewhere. Exposure will be defined as "in the same room or car with someone who has at least one puff of a cigarette or WP." WP tobacco and charcoal brands use (point of purchase, cost/gram, preferred brands and flavors and reasons for preference). Location at which most often smoked WP at home. Demographics: gender, age, race, ethnicity, age of initiation of WP use and any other tobacco product, education, income, family size and number smokers; height and weight measurement for Body Mass Index calculation (BMI = weight [kg]/height squared [m²]). Illness and Medical Care History Form (face-to-face interview), family history of pulmonary and cardiovascular diseases, cancer, lifetime and past year tobacco-related symptoms, e.g. headaches, dizziness; past year frequency of emergency room, hospitalization & other health services utilization. The 2 following forms will be used for the 3 WP smoking sessions: 7-Day Tobacco Use and Exposure Diaries (Self-administered), a 7-day 24-hour time-diary for participants on frequency, length of time and # of WP heads and/or other tobacco products smoked/exposed to indoors/outdoors by location: home/other location. WP Smoking Session Day & Exposure Form (Self-administered, RAs will complete the WP observation section), frequency, length of time and number of WPs smoked or exposed to indoors/outdoors. Location of smoking: inside home/on patio. Overall description of house: number of rooms, ventilation, windows opened, apartment/house. For WP sessions 2 and 3, open-ended questions on experience, attitudes towards and intention to future use of ice cubes in WP jar and/or use of the charcoal-free electric WP head.

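### On the visible text, heart disease, serious lung disease or past fainting after waterpipe smoking does not in itself exclude a smoker from the two charcoal sessions; three phone-checklist items would close this cheaply.

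*Combined protocol and SAP*

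**What the plan says.** The Exclusion Criteria section lists three grounds:

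- major physical or psychiatric illness that is "judged by the research assistants (RAs) to interfere with ability to give informed consent or to successfully complete an interview";
- daily waterpipe smoking, because of the wash-outs;
- pregnancy ("Pregnant women are also excluded").

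The smoker inclusion criteria cover age, smoking pattern, brand and home. The minimum frequency is that the person "smokes at least 1 WP head per month". They set no health requirement.

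Eligibility is checked by phone. Under Screening Potential Participants, the research assistants (RAs) "further determine their qualification by completing an eligibility checklist of inclusion and exclusion criteria". The Screening Form entry likewise says that the call is to "confirm eligibility using the inclusion and exclusion criteria". The contents listed for that form include no medical item.

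Sessions 1 and 2 use charcoal and Session 3 an electric head. Under Smoking Protocol, "the RAs will light a single quick-light charcoal" and place it on the loaded head. Exhaled CO is read two minutes before and after each session.

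The Illnesses form is described as covering "family history of pulmonary and cardiovascular diseases, cancer", then tobacco-related symptoms and past-year use of emergency and hospital services. The text on Session 3 places it at the final visit, "completed during the last day of the study period to avoid biasing smoking behavior".

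**The concern.** The illness exclusion tests whether a person can consent and answer questions. It does not test whether smoking a charcoal-heated waterpipe for the study is reasonable for that person. Yet the section on exhaled CO describes the hazard plainly: CO impairs oxygen delivery to the organs, can lead to syncope, and has poisoned waterpipe smokers. People with heart disease, serious lung disease or an earlier acute reaction are the ones for whom that mechanism matters most, and no visible criterion stops them from entering.

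What is at stake is participant safety, not the validity of any comparison. The study arranges these sessions, sets up the device and pays for each one. It should therefore say who ought not to take part on health grounds.

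**Working it through.** The plan gives no figure on this point to reproduce. The check is a reading of each step that could exclude such a smoker before the first session, followed by simple arithmetic on exposure.

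**Could any described step exclude the smoker?**

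1. *Inclusion criteria.* No health condition is set, so the smoker passes.
2. *Illness exclusion.* It applies only if the illness interferes with consent or an interview. A smoker with stable heart disease, for example, passes.
3. *Other exclusions.* Daily smoking and pregnancy are unrelated.
4. *Phone checklist.* It applies the same criteria. Illness may come up in the call, but it disqualifies only under step 2.
5. *Illnesses form.* Table 6 puts it on Day 8 of the weekly schedule; the Session 3 text puts it at the last visit. Either way it follows at least the first charcoal session. It does collect symptoms and emergency-room use, but it is not tied to eligibility.
6. *CO readings.* No level is given that would bar or stop a session, so as described they measure an outcome.

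On the visible text, no step excludes this person.

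**How much smoking does the study add?**

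Inputs: entry minimum 1 head per month (Inclusion Criteria for Participants); 3 session heads in 4 weeks, 2 with charcoal (Table 1 and Study Design); 7-day abstinence before each session (Day 1 – Office Visit). A month is treated as 4 weeks. Any tobacco used in the training session is not counted.

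- At the entry minimum: 3 / 1 = 3 times usual use; charcoal heads 2 / 1 = 2 times.
- At 3 heads a month: 3 − 3 = 0 added.
- Above 3 heads a month: the scheduled heads add none, and the wash-outs may lower the total.

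Sessions 1 and 2 fall on day 7 of weeks 1 and 2, that is, study days 7 and 14. The two charcoal heads are therefore 14 − 7 = 7 days apart.

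**How many extra people would a screen need?**

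Let p be the share answering yes to any item. Extra people needed to enrol 50 smokers = 50 / (1 − p) − 50. The documents do not give p; 2% to 10% is assumed.

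- p = 2%: 50 / 0.98 − 50 = 1.0
- p = 10%: 50 / 0.90 − 50 = 5.6

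That is about 1 to 6 people.

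**The case against.** The strongest reply is that these people smoke waterpipe at home anyway, a full head at a time, and are asked to smoke in their usual manner. Having an RA light the charcoal is standardisation and adds no hazard of its own. An RA also observes the session and reads CO. Most of this stands, and it is why the added risk is called limited. It does not cover the smoker near 1 head per month, for whom the study raises frequency.

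A second reply is that a screen or warning may exist elsewhere. The IRB correspondence lists a screen form, the plan refers consent detail to a human-subjects form, and the principal investigator helps to qualify participants. This also stands: a reader might infer that the study has no health screen at all, and the documents cannot support that. The point concerns the stated criteria, from which the checklist is built.

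Two figures invite a stronger reading. One is the 50 × 2 = 100 charcoal sessions. That counts every smoker's sessions, not those of people with these conditions, whose number is not given. The other is the cited mean expired CO of 32.9 ppm after waterpipe against 7.4 ppm with cigarettes (32.9 / 7.4 = 4.4 times). The relevant contrast is study smoking against the participant's own usual waterpipe smoking, and the documents give no figure for that. Neither number measures added harm.

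The pregnancy exclusion shows only that a criterion unrelated to interview capacity already has a place in the list. The plan gives no reason for it, so it is not evidence of a safety rule left half finished.

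Finally, the Illnesses form was put last on purpose, so as not to influence smoking, and a question on past fainting brings some of that content forward. This is a fair cost, taken up under the fix.

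**Conclusion.** The point holds as a modest safety gap in the visible eligibility text. A smoker with diagnosed heart disease, serious lung disease, or past fainting or emergency care after waterpipe smoking is not excluded on that ground from two charcoal sessions, although the plan names the CO hazard itself.

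Its size is limited. For a smoker at the entry minimum, the study schedules 3 times the usual number of heads and 2 times on charcoal heads alone; for a smoker of 3 or more heads a month, the scheduled sessions add none. How many enrolled smokers would have one of these conditions is unknown.

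The conclusion assumes that the unseen screening, consent and human-subjects material does not already bar these smokers. A reader should not infer that any Aim 1 or Aim 2 result is wrong: the gap concerns who is exposed, not how sessions are compared. It is worth correcting because the correction is cheap.

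**What to change.** Add to the Exclusion Criteria, for smokers only, self-report of any of:

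- (a) doctor-diagnosed heart disease;
- (b) doctor-diagnosed chronic obstructive pulmonary disease or other serious lung disease (mild asthma alone does not exclude);
- (c) past fainting or emergency care after waterpipe smoking.

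Ask these as three neutrally worded yes/no items on the existing phone checklist; any yes means not eligible. Keep the Illnesses form on the last day. If the unseen material already contains such a screen, state it in the criteria too.

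Costs: three questions on a call already planned, with no new visit, form or assay, and the few extra people calculated above. Results would no longer describe smokers with these conditions.

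Slight sensitisation is possible. It is tempting to say that it cancels within smoker because the items are asked once, before all sessions. The design does not support that. Session order is fixed, so an effect that fades could be strongest at Session 1, which is the Aim 1 reference and the only Aim 2 session. The protocol should call the effect probably small, and should not claim that it is equal across configurations.

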face using the Tobacco Use History Questionnaire; explain how to complete the diaries on a daily basis; explain the urine collection protocol (2 first morning urine samples/smoking session); provide each participant with 2 coded empty urine cups (no names on urine cups and forms), gloves, 2 zip-lock bags/urine cup; ask participants to store the double sealed urine samples once obtained in his/her personal refrigerator (freezer section) until pickup by RAs the next day. Arrange for the smoking session and home visit on day 7 of the first week study period. The PI and SC will accompany the RAs to their first two homes (more if needed) for hands-on training for data collection. Wash-out period: smokers will abstain from smoking and exposure to any tobacco smoke for 7 days prior to each smoking session. WP smokers will choose a WP smoking day to start the 4-week study period; the RAs will coordinate the Office Visit accordingly. Non-smokers will choose any day to provide 2 first urine samples on two consecutive days. Saliva Test: Trained by the PI, the RAs will use NicAlert to validate non-smoking status, and as a bogus pipeline technique, which we used successfully in our previous studies. NicAlert, a commercial semi-quantitative instant saliva cotinine test, is accurate and valid with high sensitivity (93-100%) and specificity (95-96%) Non-smoking participants will be informed about the purpose of the NicAlert test during the informed consent process. (Appendix K. Saliva Test Procedure) Days 2 - 6: The RAs will contact participants by phone on the 4th day to confirm adherence to the 7-wash-out period and diaries, and on the 6th day to remind participants to collect the first morning urine sample on day 7, and to arrange for a home visit for the first WP smoking session. Day 7: Waterpipe smoking session 1. WP smokers will provide one first morning urine sample and store it in their refrigerator (freezer section). Participants from our previous WP studies stored their urine samples, double bagged in their refrigerator. WP smokers will smoke WP tobacco (10 grams) as they normally do using charcoal and room temperature water in the water jar. The RAs will collect expired CO levels 2 minutes before and 2 minutes after concluding smoking. Day 8: Participants will provide a first morning urine sample. The RAs will pick up the 2 urine samples (frozen), place them in a cooler (to transfer them to our research center laboratory for aliquoting and storage in a freezer at -20°C to be sent out for analyses); pick up the diaries and Waterpipe Smoking Session Day and Exposure From, arrange for the 2nd WP smoking session home visit, provide forms, urine cups package for week 2 of the study.

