Furan is oxidized to a reactive α , β -unsaturated dialdehyde, *cis*-2-butene-1,4-dial (BDA), a toxic metabolite of this liver toxicant and carcinogen. It has been determined that there is a strong relationship between Furan-BDA-NAL and smoking. Levels of urinary Furan-BDA-NAL, a BDA derived metabolite of furan, were higher in cigarette smokers relative to those in nonsmokers. We will measure sulfides 2 and 4; sulfoxides 3 and 5 and BDA-NAL: 1 and 6. In small sample sizes (N=5, N=16), furan metabolite sulfoxide 3 ranged from 8.7 to 69 pmol/mg creatinine among cigarette smokers and from 1.4 to 6.5 pmol/mg creatinine, with LOQ of <.02. We will be the first to determine the levels of Furan-BDA-NAL in WP smokers, thereby assessing WP smokers' potential health risks associated with furan exposure.

Laboratory Analyses for the Proposed Urinary Biomarkers.

Dr. [name] laboratory at The Masonic Cancer Center, University of Minnesota, will conduct the following laboratory urine analyses, as described previously: NNAL with a LOQ of 1.672 pg/mL (0.01 pmol/mL), 1-HOP with a LOQ of (0.05 pmol/mL), SPMA with a LOQ of 0.03 pmol/mL, Furan-BDA-NAL with a LOQ of <.02 pmol/mg creatinine). [name] at SDSU will conduct laboratory urine analyses for cotinine with a LOQ of 0.1 ng as described previously; and will conduct laboratory analyses for creatinine for normalization.

Gender Representation. Efforts will be made to recruit equal samples of males and females.

Participants Retention and Incentives. Flexible scheduling for study activities where applicable. Following completion of study activities, a \$75 check issued by SDSU will be mailed to non-smokers, and \$250 to smokers: \$100/smoking session and \$25/ training session. Proration will apply for completed activities.

Study Timeline. (Table 3) In the first 3 quarters of Year 1 we will develop forms and procedure manuals, hire and train staff, pilot test and refine protocols and study measures, and obtain IRB approval. Sequential recruitment of participants, data collection, urine aliquoting, data entry, cleaning and coding will start during the 4th quarter of Year 1, and continue through the end of year 2. We expect we will need about 15 months to complete data collection in naturalistic settings. Data analysis and manuscript preparation will start in year 3. Dissemination of results will start in Year 3.

Table 3. Timeline	1			2	3
Forms Procedures manual development					
Hire and train staff					

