Aim 1 calls for comparing pre/post session change in exhaled CO, and in urinary levels of cotinine, NNAL, SPMA, and 1-HOP in first morning urine samples the morning of, and the morning after, each of 3 WP smoking sessions at home: (Session 1) using charcoal to heat the tobacco and only water in the jar; (Session 2) using charcoal to heat the tobacco and adding ice cubes in the jar; and (Session 3) using electrically heated tobacco and only water in the jar. Among smokers, differences in pre/post change on CO and each biomarker between sessions 1 & 2, and between sessions 1 & 3, will be assessed by mixed regression models to handle repeated measures on each participant. Demographics, duration of smoking, and possible confounding factors, such as number of smokers inside the home and years smoked, will be included as covariates.

Power analysis. As no data exist on effect sizes of differences between session configurations for Aim 2, in Table 4 we show estimated power to detect difference for a range of potential intra-class correlations (ICC) and an effect size of .40 (medium by Cohen's criteria), based on paired z-test, n=50, two-sided alpha=.05. Estimates are conservative, since addition of covariates and adjustment for pre-session CO or urinary biomarker levels in the analyses will increase power.

Table 4. Power				
estimate	es			
Effect	ICC	Darran		
Size	icc	Power		
0.40	0.25	0.637		
0.40	0.50	0.807		
0.40	0.75	0.979		

Aim 2 will examine levels of urinary Furan-BDA-NAL following the analysis strategy described in Aim 1, but using data only from Session 1, the configuration commonly practiced in naturalistic settings, using charcoal to heat the tobacco, and room temperature water in the jar. We will begin with a comprehensive descriptive analysis of demographics and Furan-BDA-NAL levels and their distribution in WP smoker participants. As in Aim 1, analyses will identify differences in metabolite levels between smokers vs. non-smokers, and between pre vs. post WP smoking Session 1, for the sample overall as well as by demographic categories (age, gender, BMI). Pearson's correlations will be conducted between urinary levels of Furan-BDA-NAL and values of other metabolites (cotinine, NNAL, SPMA, and 1-HOP) quantified for WP smoking Session 1.

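### The clock time of the smoking sessions is neither fixed nor matched within smoker, so the interval from session to Day 8 urine is free to vary and the Aim 1 models do not name it

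*Combined protocol and SAP*

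**What the plan says.** The post-session sample is tied to the calendar, not to the session. Under Waterpipe Smoking Session 1 the plan reads "Day 8: Participants will provide a first morning urine sample", and Aim 1 compares urinary levels "in first morning urine samples the morning of, and the morning after, each of 3 WP smoking sessions at home".

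The session itself has a day but no hour. In the same Session 1 section, "WP smokers will choose a WP smoking day to start the 4-week study period". At the end of the first week the research assistants (RAs) "arrange for the 2nd WP smoking session home visit", and session 3 is arranged in the same way. No section gives a start time, a window, or a requirement that sessions 2 and 3 match session 1.

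The section on standardised setting aims to reduce variance from factors outside the configurations. It says "we will standardize setting the WP device, aluminum foil, and amount, type and brand of WP tobacco and quick-light charcoal", and adds water and ice volumes. Elsewhere the plan also fixes a 7-day wash-out, one head per session, no sharing and no other smoker present. Time of day is not among the controlled factors.

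On recording, the Smoking Protocol has the RAs "complete the WP session observation form, such as length of time smoking, etc". On analysis, Aim 1 states "Demographics, duration of smoking, and possible confounding factors, such as number of smokers inside the home and years smoked, will be included as covariates". Exhaled CO, by contrast, is measured 2 minutes before and 2 minutes after each session.

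**The concern.** Aim 1 is a within-person comparison of pre-to-post rises, session 1 against 2 and session 1 against 3. Suppose a marker is cleared over hours, and a smoker has one session in the late evening and another in the late morning. The two Day 8 voids then catch different fractions of the rise even if the configurations deliver the same dose. Person-level covariates cannot absorb a difference between sessions within a person, and duration of smoking measures something else.

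Two consequences need to be kept apart. If start times vary without pattern, the result is noise. If they move on average between sessions, the result is bias. Under Study Design every smoker has charcoal with water, then ice, then the electric head, so a shift in booking hour would coincide with configuration. The plan expects lower SPMA and 1-HOP with the electric head; earlier electric sessions would push the urinary levels the same way.

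**Working it through.** **1. The plan's own figure.** Table 4 uses a paired z-test, effect size d = 0.40, n = 50, two-sided alpha 0.05.

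Power = Φ(d√n / √(2(1 − ICC)) − 1.96)

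This gives 0.637, 0.807 and 0.979 at ICC 0.25, 0.50 and 0.75. Table 4 is reproduced.

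**2. Inputs from the documents.** The SPMA paragraph gives geometric means of 0.26 before and 0.58 after a home session (95% CI after: 0.40 to 0.83; N = 50).
- Log-SD after the session: ln(0.83/0.40) / (2 × 1.96) × √50 = 1.317.
- The 0.40 SD planning effect is 0.40 × 1.317 = 0.53 log units, a ratio of about 1.69.
- Smoke-related share of the post level: (0.58 − 0.26)/0.58 = 0.55.

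**3. Assumptions.** The documents give neither half-lives nor start times. I assume first-order decay with half-life T from 6 to 24 h, in two versions:
- (a) the whole post level decays, which is a bound;
- (b) only the smoke-related rise decays, which is more realistic.

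The effect per hour of interval, in SD units, is ln 2/(T × 1.317) under (a), and 0.55 times that under (b). Version (b) is a first-order approximation around the post level.

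**4. Unsystematic variation.** Let start times vary independently with an SD of 4 h per session, and let v be the square of (4 × effect per hour). Power becomes Φ(0.40√50 / √(2(1 − ICC) + 2v) − 1.96).

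| T = 6 h | ICC 0.25 | ICC 0.50 | ICC 0.75 |
|---|---|---|---|
| Table 4 | 0.637 | 0.807 | 0.979 |
| (a) | 0.572 | 0.717 | 0.906 |
| (b) | 0.616 | 0.779 | 0.962 |

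The largest loss is 0.807 − 0.717 = 0.09. At T = 12 h or more the loss is at most 2.3 points under (a) and under 1 point under (b).

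**5. Systematic shift.** Let one session run on average 4 h earlier or later than session 1, with no true difference. Under (b), bias = 4 × 0.693 × 0.55/(T × 1.317). The false-positive rate at ICC 0.50 follows from the non-centrality bias × √50 / √(2 × 0.50).

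| T | Bias (SD) | False-positive rate |
|---|---|---|
| 6 h | 0.19 | 0.28 |
| 9 h | 0.13 | 0.15 |
| 12 h | 0.10 | 0.11 |
| 24 h | 0.05 | 0.06 |

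Under the bound (a) the bias is 0.35, 0.23 and 0.18 SD at 6, 9 and 12 h. None reaches 0.40 SD.

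**6. Long-lived markers.** At T = 40 h a 12 h gap changes the level 2^(12/40) = 1.23-fold even under (a); at 240 h, 1.04-fold.

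**Limits.** The decay model ignores voids between the session and the morning. It applies the SD of a post level to a change outcome. The cited SPMA study's sampling interval is not given, so its SD may already contain some timing noise.

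**The case against.** The strongest reply is that the gap may be small in practice and partly covered.

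- **Habit.** Smokers are asked to smoke at home as usual and may keep a habitual hour. The sentence "Flexible scheduling for study activities where applicable" concerns retention and does not say that session hours will move. Nothing in the documents points to a drift between sessions, and training on the electric head is a separate visit. This stands: the interval is free to vary, but is not shown to vary.
- **Size.** A reader might infer that timing can rival the configuration effect. For one smoker with a 10 h shift, version (b) computed exactly, as ln(0.58/(0.26 + 0.32 × 2^(−10/T))), gives 0.47, 0.35, 0.28 or 0.15 log units at T = 6, 9, 12 or 24 h. That is 90%, 67%, 53% or 28% of 0.53. But the 0.40 SD in Table 4 is a mean difference over 50 smokers, so the sample's average start would have to move by about 10 h. The documents do not support that.
- **Recoverability.** A reader might also infer that timing could never be checked afterwards. The 24-hour time-diary covers Days 7 and 8, the RA form is described with an open list, and RAs are present to time the CO readings. Session times may therefore exist. No section says that the Day 8 void time is recorded, however.
- **Open covariate list.** Aim 1 names possible confounders by example, so the interval is unnamed and not excluded. Leaving it to later choice is still weaker than prespecifying it.
- **Aim 2.** It uses Session 1 only, so the between-session argument does not extend to it.

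**Conclusion.** The concern holds as a gap in control, at moderate weight. The documents fix the post-session urine to the Day 8 first void, leave the session hour open for each session, and do not name the interval in the Aim 1 models. Exhaled CO is not affected.

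For shorter-lived urinary markers, unpatterned timing is a modest loss of precision. The more serious risk is conditional. If booking hours shift on average between sessions, the fixed order makes the resulting bias inseparable from configuration, and it need not approach 0.40 SD to inflate false positives well above 5%. Whether such a shift would occur is unknown. The sizes rest on assumed half-lives, an assumed 4 h shift or spread, and SPMA figures from the sponsor's earlier home study.

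**What to change.** - **Smoking Protocol:** book each smoker's sessions 2 and 3 within a common clock window around that smoker's session 1 start. The sponsor should choose the width; no calculation here dictates it.
- **Recording:** enter the session end time on the RA observation form, and have the participant write the Day 8 void time on the cup label.
- **Aim 1:** add hours from session end to Day 8 void as a session-level covariate in the urinary biomarker models, or prespecify it as a sensitivity analysis.

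The cost is two clock times, one model term and slightly less flexible booking. If the booking rule is refused, recording and adjusting alone costs very little, although adjustment is a weaker safeguard than matching if the interval tracks configuration closely. Void times need to be captured as samples are collected, so the change belongs before fieldwork.
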